Lastly, recent evidence demonstrates that loco-regional curative treatment with stereotactic ablative radiotherapy (SABR) is a good alternative as compared with conventional 3D RT for patients with solid tumour, with durable remissions and a low toxicity profile. Many non-randomised studies have shown that SBRT for oligometastases is safe and effective, with local control rates of about 80%. Importantly, these studies also suggest that the natural history of the disease is changing, with 2–5 year progression-free survival of about 20% [Tree]. For colorectal, non-small cell, and renal cell cancers, 1-year metastasis control rates ranged from 67 to 91% [Salama]. Moreover, abscopal reponses in the setting of immune checkpoints inhibitors and radiotherapy combinations have been made in the setting of metastatic disease event in patients with extensive tumor burden [Postow], [Golden], [Reynders]. The goal of SABR is to deliver appropriate metastasis directed radiotherapy while minimizing exposure of surrounding normal tissues. Interestingly, the dose and fractionation employed modulate RT

ability to synergize with immunotherapy. Vanpouille-Box et al, showed that immune response genes were differentially expressed in irradiated tumours by 8Gyx3 but not 20Gyx1. This highlight the interest of hypofractionated SABR acting as a "in situ tumour vaccine" [Vanpouille-Box].

As hypofractionated SABR may, in addition to its good local control, increase the effectiveness of anti PD-L1, we aimed to investigate the efficacy and the tolerability of the combination of anti-PD-L1 antibody with SABR. Preliminary clinical data about the combination of Atezolizumab and radiotherapy in metastatic patients suggest that irradiation of one tumor site may induce disease stabilization which may last several Atezolizumab administration cycles (ie 3-6 months). These early data might reflect the fact that the systemic anti tumor response is transient. Thus, we plan to test whether focal re irradiation of a previously un irradiated tumor site might re induce systemic anti tumor response in the case of disease re evolution for patients progressing after initial stabilization of their disease. These data are in line with one of the first prospective clinical trial aimed at evaluating abscopal effect which performed radiation therapy to 2 distinct tumor sites separated from several weeks [Golden].

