2.2 Secondary objectives

To determine, the progression-free survival (PFS) measured from the date of treatment initiation to the date of death or progression, whichever comes first under combined SABR and anti-PDL1 atezolizumab therapy using RECIST v 1.1 and modified RECIST (mRECIST).

To further describe, the efficacy of combination (SABR and atezolizumab) both on the irradiated lesions and the non-irradiated lesions based on tumour response indicators and clinical endpoints using RECIST 1.1 criteria and modified RECIST (mRECIST).

To determine the Treatment failure rate defined as the proportion of patients who cannot receive the planned irradiation dose or relative atezolizumab dose intensity below 75% of the initially targeted dose (i.e below 900 mg).

To evaluate the toxicity of atezolizumab in combination with SABR according to the NCI-CTCAE scale (version 4.03).

To assess tumor reponse indicators and clinical endpoints, assessed according to RECIST v1.1 at 6 weeks after the second SABR course.

In lung and sarcoma patiens who received a second SABR course after oligoprogression:

- To assess the objective response rate at 6 weeks after the second SABR course, using RECIST v1.1 and continuation of atezolizumab at the time of progression.
- To compare the modification of the size of the lesion which received the second SABR course versus the non-treated lesion (abscopal effect). Modification is assessed as the variation between the size at the time of the second SABR course and the size 6 weeks thereafter.
- To assess progression-free survival 2 (PFS2) measured from the date of the second SABR course to date of second progression or death whichever comes first. Patients alive and free of progression at the cut-off date will be censored at the last assessment date.
- Time to progression ratio (TTPr) in patient receiving a second SABR course:

To define the TTP ratio, let's denote:

- TTP1 the time from treatment initiation to the time of progression after first irradiation.

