7.2 Secondary criteria

7.2.1 Efficacy

- Progression-free survival (PFS) measured from the date of treatment initiation to the date of progression or death, whichever comes first. Patients alive and free of progression at the cut-off date will be censored at the last assessment date.
- Modification of the size of the irradiated and non irradiated lesion(s) as measured by its longest diameter according to RECIST 1.1 will be compared.

Assessment of efficacy endpoint listed below will be performed according to RECIST v 1.1 criteria (refer to Appendix 4: RECIST 1.1 CRITERIA) and modified RECIST (mRECIST) (refer to Appendix 5: mRECIST CRITERIA MODIFIED RESPONSE EVALUATION CRITERIA IN SOLID TUMORS).

Efficacy endpoints are:

- Disease Control Rate (DCR): complete responses (CR) + partial responses (PR) + stable disease (SD).
- Objective Response Rate (ORR): CR + PR
- Duration of response (DOR)
- Time to progression (TTP) of non irradiated lesions is computed as the delay from enrollment to the first occurrence of progression outside of the irradiated field
- Time to progression (TTP) of irradiated lesions is computed as the delay from enrollment to the first occurrence of progression of irradiated lesions;
- Evaluation of the local control, distant control.

In lung cancer and sarcoma patients receiving a second SABR course:

For patients in lung and sarcoma cohorts who can receive a second SABR course if oligoprogression, the objective response rate at 6 weeks is defined as any partial or complete response according to RECIST v1.1 observed at the first radiological evaluation (6 weeks after the second SABR course) over the number of patients that received a second SABR course.

- Size of the irradiated and non irradiated lesion(s) is measured in its longest diameter according to RECIST 1.1. Modification observed between the time of progression 1 and the value at 6 weeks will be compared between irradiated and non irradiated lesions.

- Progression-free survival 2 (PFS2) measured from the date of the second SABR course to the date of second progression or death. Patients alive and free of progression at the cutoff date will be censored at the last assessment date.
- Time to progression ratio (TTPr) in patient that received a second SABR course. To define the TTP ratio, let's denote:
 - o TTP1 the time from treatment initiation to the time of progression after first irradiation

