 - TTP2 the time from first progression to the time of progression after the second SABR course. Patients alive and free of progression at the cut-off date will be censored at the last assessment date. Radiological progression is measured using recist v1.1 on the same tumor lesions over all the trial whenever possible. TTP2 is defined as PFS2 as it is unlikely that patients die of cause unrelated to the treatment failure and subsequent tumor progression.

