20 APPENDIX 4: RECIST 1.1 CRITERIA

The criteria below are based on RECIST 1.1. (Eisenhauer EA et al.Eur J Cancer 2009;45:228-247)

Measurability of the disease

Measurable disease: Measurable disease requires the presence of at least one measurable lesion. If the measurable disease is restricted to a solitary lesion, its neoplastic nature should be confirmed by cytology/histology.

Measurable lesions:

- Lesions that can be accurately measured in at least one dimension with longest diameter ≥ 10 mm (by CT scan, MRI, caliper measurement) or ≥ 20 mm (by chest X-ray). Longest diameter will be recorded.
- For a lymph node to be considered pathologically enlarged and measurable, the short axis must be ≥15 mm (by CT scan). The short axis will be recorded.

Non-measurable disease:

- Non-measurable lesions are all other lesions, including small lesions (longest diameter <10 mm with CT scan, MRI or caliper measurement or <20 mm with chest X-ray or pathological lymph nodes with shortest axis ≥10 and <15 mm) as well as truly non-measurable lesions. Lesions considered truly non-measurable include leptomeningeal disease, ascites, pleural or pericardial effusion, inflammatory breast disease, lymphangitic involvement of skin or lung, abdominal masses/abdominal organomegaly identified by physical exam that is not measurable by reproducible imaging techniques.

- New lesions in irradiated fields
- Previously irradiated lesions should not be used as indicator lesions. However, new lesions occurring in previously irradiated fields can be used to assess the anti-tumour response.

Methods of measurement

All measurements must be recorded in metric notation, using a ruler or calipers. All baseline evaluations must be performed as close as possible to the treatment start and within 4 weeks before the beginning of the treatment. If a lesion is considered too small to measure, a default measurement of 5 mm should be applied. If the lesion is not visible, a default measurement of 0mm should be applied.

The same method of assessment and the same technique must be used to characterise each identified and reported lesion at baseline and during follow-up.

Clinical lesions will only be considered measurable when they are superficial (e.g., skin nodules, palpable lymph nodes). In the case of skin lesions, documentation by colour photography including a ruler to estimate the size of the lesion is suggested.

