CT and MRI are the best currently available and reproducible methods to measure target lesions selected for response assessment. Conventional CT and MRI should be performed with cuts of 5 mm or less in slice thickness contiguously. Spiral CT should be performed using a 5 mm contiguous reconstruction algorithm. This applies to the chest, abdomen and pelvis.

Ultrasound, endoscopy and laparoscopy should not be used to measure tumour lesions or evaluate tumour response. However, these techniques can be useful to supplement information from other techniques.

Tumour markers alone cannot be used to assess response. If markers are initially above the upper normal limit, they must normalise for a patient to be considered in complete clinical response.

Cytology and histology can be used to differentiate between PR and CR in rare cases (for example, residual lesions in tumour types such as germ cell tumours, where known residual benign tumours can remain).

Baseline Documentation of Target and Non-target Lesions

All measurable lesions up to a maximum of two lesions per organ and five lesions in total, representative of all involved organs should be identified as target lesions and will be recorded, measured and numbered at baseline. The longest diameter will be recorded, except for lymph nodes, which will be measured by their short axis. Target lesions should be selected on the basis of their size (lesions with the longest diameter) and their suitability for accurate repetitive measurements (either by imaging techniques or clinically).

The sum of diameters for all target lesions will be calculated and reported as the baseline sum of diameters. The baseline sum of diameter will be used as reference to further characterize the objective tumour response of the measurable dimension of the disease (Table 1.1).

Table 1.1: Evaluation of target lesions

Complete Response (CR)	Disappearance of all target lesions. Any pathological lymph nodes (whether target or non-target) must have a reduction in short axis to <10mm)
Partial Response (PR)	At least a 30% decrease in the sum of diameters of target lesions, taking as reference the baseline sum diameters

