Progression (PD)	At least a 20% increase in the sum of diameters of target lesions, taking as reference the smallest sum on study (this includes the baseline sum if that is the smallest on study). In addition to the relative increase of 20%, the sum must also demonstrate an absolute increase of at least 5 mm. (Note: The appearance of one or more new lesions is also considered progression.)
Stable Disease (SD)	Neither sufficient shrinkage to qualify for PR nor sufficient increase to qualify for PD, taking as reference the smallest sum diameters while on study.

All other lesions (or sites of disease) should be identified as non-target lesions and should also be recorded at baseline. Measurements are not required and these lesions should be followed as "present" or "absent" (Table 1.2).

Table 1.2.: Evaluation of non target lesions

Complete Response (CR)	Disappearance of all non-target lesions and normalisation of tumour marker level. All lymph nodes must be non-pathological in size (<10mm short axis)
Non-CR / Non-PD	Persistence of one or more non-target lesions and/or maintenance of tumour marker level above normal limits
Progression (PD)	Unequivocal progression (see comments below) of existing nontarget lesions. (Note: the appearance of one or more new lesions is also considered progression).
	Although a clear progression of non-target lesions only is exceptional, in such circumstances, the opinion of the treating physician should prevail and the progression status should be confirmed later by the review panel (or study chair).

In some circumstances it may be difficult to distinguish residual disease from normal tissue.

When the evaluation of complete response depends upon this determination, it is recommended that the residual lesion be investigated (fine needle aspirate/biopsy) before confirming the complete response status.

Evaluation of Best Response to Study Treatment

The best response to study treatment (Table 1.3) is the best response recorded from the start of treatment until disease progression or start of further anti-cancer treatment (taking as reference for progressive disease the smallest measurements recorded since the treatment started). In general, the patient's best response assignment will depend on the achievement of both measurements and confirmation criteria.

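### The 6-week response after the second SABR course has no reference scan, and the RECIST rules supplied default to the pre-treatment baseline, so the count partly reflects the first course

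*Protocol*

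**What the plan says.** Section 7.2.1 defines the objective response rate after the second course as "any partial or complete response according to RECIST v1.1 observed at the first radiological evaluation (6 weeks after the second SABR course"), taken "over the number of patients that received a second SABR course". It does not say against which scan the response is measured.

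The RECIST 1.1 rules the protocol supplies are in Appendix 4:

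- Timing of baseline: "All baseline evaluations must be performed as close as possible to the treatment start and within 4 weeks before the beginning of the treatment".
- Partial response: "At least a 30% decrease in the sum of diameters of target lesions, taking as reference the baseline sum diameters".
- Progression: an increase of at least 20% and at least 5 mm over the smallest sum on study. A new lesion makes the overall response progression whatever the target lesions do (Tables 1.1 and 1.3).

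No section sets a new baseline or re-selects target lesions at first progression. For time to progression after the second course, 7.2.1 leans the other way: "Radiological progression is measured using recist v1.1 on the same tumor lesions over all the trial whenever possible".

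Section 8.1 gives this endpoint its own test in each of the lung and sarcoma cohorts: p0=10%, p1=30%, one-sided alpha 10%, power 90%, 25 to 30 patients. Five or more responses are called promising, and the threshold is to be recomputed at the actual number re-irradiated.

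The neighbouring lesion-size endpoint does have a later reference, but it is worded in two ways. Section 2.2 says "Modification is assessed as the variation between the size at the time of the second SABR course and the size 6 weeks thereafter", while 7.2.1 starts from the time of progression 1.

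**The concern.** A second course is given only after first progression by RECIST 1.1. The stated purpose is to see whether "focal re irradiation of a previously un irradiated tumor site might re induce systemic anti tumor response". A response count for that purpose should measure change from the disease present when the second course starts.

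Under the Appendix 4 defaults, the reference for partial response lies before the first atezolizumab dose, and the reference for progression is the best point reached during the first course. The shrinkage needed to count as a responder then depends on what happened before the second course. Some patients cannot score a response; others need almost no change to score one. Both kinds enter the same count, which is compared with a fixed threshold, so the stated error rates no longer describe a decision about the second course.

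**Working it through.** **1. The plan's decision rule reproduces.** Inputs from section 8.1: p0=0.10, p1=0.30, n=25, promising if X ≥ 5, with X exact binomial.

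- P(X ≥ 5 | 25, 0.10) = 0.098, within the 10% limit.
- P(X ≥ 5 | 25, 0.30) = 0.9095, as stated.
- At n=30, a threshold of 5 gives alpha 0.1755. A threshold of 6 gives 0.0732 with power 0.9234, and the planned recomputation covers this.

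The sample-size arithmetic is not at fault.

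**2. Shrinkage needed for partial response under Appendix 4.** Illustrative pre-treatment sum: 100 mm. To score partial response, the 6-week sum must be ≤ 70 mm and must no longer meet the progression rule against nadir. If first progression occurs exactly at 1.2 × nadir, the required fall from that scan is:

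| Nadir (mm) | Sum at first progression (mm) | Condition for PR at 6 weeks | Fall needed |
|---|---|---|---|
| 100 | 120 | ≤ 70 mm | 1 − 70/120 = 41.7% |
| 80 | 96 | ≤ 70 mm | 1 − 70/96 = 27.1% |
| 60 | 72 | ≤ 70 mm | 1 − 70/72 = 2.8% |
| 50 | 60 | < 60 mm | any fall |

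- Row 1: a true 30% fall gives 120 × 0.7 = 84 mm, which is 16% below baseline, so it scores as stable disease.
- Row 4: 59 mm is 41% below baseline, and 59/50 = 1.18, i.e. 18% above nadir, so it is not progression. It scores partial response after a fall of 1/60 = 1.7%.
- Row 4 with no change: 60 mm is still 20% and 10 mm above nadir, so it stays progression.
- A sum beyond the progression threshold needs more: with nadir 40 mm and 55 mm at progression, the sum must fall below 48 mm, about 12.7%.

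**3. New lesions.** The Synopsis defines oligoprogression as at most 3 extracranial sites of progressive disease and does not restrict it to target lesions. Under Table 1.3, a patient whose first progression included a new lesion remains progression while that lesion is visible, whatever the target sum does. If the new or non-target lesion resolves and the target sum was already ≤ 70% of baseline, the patient can score partial response with an unchanged target sum.

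**4. Effect on the rule.** The documents give no share for either kind of patient, so these are assumed ranges at n=25, threshold 5.

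A share f cannot score a response and the rest respond at 30%, so p = 0.30(1 − f):

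| f | 0 | 10% | 20% | 30% |
|---|---|---|---|---|
| Power | 0.91 | 0.85 | 0.75 | 0.63 |

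A share g scores partial response by carry-over and the rest respond at 10%, so p = g + 0.10(1 − g):

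| g | 0 | 5% | 10% | 15% |
|---|---|---|---|---|
| Chance of promising | 0.10 | 0.29 | 0.53 | 0.73 |

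For example, f=20% gives p=0.24, and g=10% gives p=0.19. At n=30 with threshold 6 the same two cases give 0.76 and 0.52.

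**The case against.** The strongest reply is that 7.2.1 never says the pre-treatment baseline applies. It says RECIST v1.1 at 6 weeks, and the other second-course measures (lesion size, PFS2) are referenced to first progression or the second course. A statistical analysis plan might name the scan. It is true that the pre-treatment reference is a default from Appendix 4, not a statement in 7.2.1. But the definition, the RECIST rules and the decision threshold all sit in the protocol, and followed as written they give the results above.

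Four stronger readings are tempting and do not hold.

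- *An unchanged sum after a deep response counts as a response.* Where the target sum itself progressed, it does not: the nadir rule keeps it at progression.
- *Nobody can respond, because Appendix 4 records* "the best response recorded from the start of treatment until disease progression or start of further anti-cancer treatment". That sentence defines best response over study treatment, not response at one time point. Applied here it would contradict a test of 10% against 30%.
- *Every patient with a new lesion scores zero.* This holds only while the lesion persists, and the re-irradiated lesion may be that one.
- *The decision rule should rest on non-irradiated lesions only.* Nothing excludes re-irradiated lesions from the sum, and two equal 30 mm targets with one falling 60% give a 30% fall overall. But overall response is a stated objective, and the abscopal question has its own size comparison. Moving the rule would create a different endpoint needing its own p0 and p1.

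The endpoint is also secondary, and the label is promising, not a stopping or continuation rule. The two size references will usually point to the same scan, since Table 1 places the second course at first progression without a separate scan.

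**Conclusion.** The point holds as a defect in the endpoint definition. No reference scan is fixed, and the protocol's own RECIST rules default to one that predates the first course. The fall that earns a partial response runs from 41.7% to under 2% according to first-course history, and a persisting new lesion rules out a response altogether. The error rates of the 5-response rule are therefore not secured. How far they move depends on shares the documents do not give, so the power and false-positive figures are illustrations, and the two distortions act in opposite directions. The primary one-year endpoint is untouched. The differing size references in 2.2 and 7.2.1 are a minor inconsistency to settle at the same time.

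**What to change.** In 7.2.1 and 8.1, define the 6-week response against the last scan before the second course, normally the one documenting first progression. Re-select target lesions at that scan, including measurable new lesions, and define partial response as a fall of at least 30% from that sum. Lesions present at the reference scan then no longer count as new. State how patients with no measurable lesion at that scan are scored, since the denominator is everyone given a second course.

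Use the same reference scan for lesion size in 2.2 and 7.2.1. Keep the decision rule on overall response, with p0, p1 and the threshold as planned, and report response excluding re-irradiated lesions as a supportive result.

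The cost is wording plus re-derivation. Appendix 4 does not require non-target lesions to be measured, so some non-target or new lesions may have to be measured on existing scans. The change should be made before the second-course responses are tabulated.

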Primary evaluation criterion	One year-Progression-free survival rate is defined as the rate of patients alive and free of progression at one year. Progression is defined using RECIST 1.1. criteria, or death, whatever the cause of death, whichever occurs first.
Secondary	Efficacy:
evaluation criteria	Progression-free survival (PFS) measured from the date of treatment initiation to date of progression or death whichever comes first. Patients alive and free of progression at the cut-off date will be censored at the last assessment date
	Tumour response indicators and clinical endpoints, assessed according to RECIST v 1.1 and modified RECIST are:
	- Disease Control Rate (DCR): complete responses (CR) + partial responses (PR) + stable disease (SD).
	- Objective Response Rate (ORR): CR + PR
	- Duration of response (DOR)
	- Time to progression of non-irradiated lesions is computed as the delay from enrollment to the first occurrence of progression outside of the irradiated field
	- Time to progression of irradiated lesions is computed as the delay from enrollment to the first occurrence of progression of irradiated lesions;
	- Evaluation of the local control, distant control.
	Toxicity: NCI- CTCAE V4.03 scale Toxicity is adverse events graded with the NCI-CTC-AE v4.03 scale, at least possibly related to the treatment.
	For patients with lung cancer and sarcoma receiving a second SABR course for oligoprogression:
	- Progression-free survival 2 (PFS2) measured from the date of second SABR course to date of second progression or death whichever comes first. Patients alive and free of progression at the cut-off date will be censored at the last assessment date.
	- Tumor response indicators and clinical endpoints, assessed according to RECIST v1.1 at 6 weeks after the second SABR course.
	Time to progression ratio (TTPr) in patient receiving a second SABR course:
	- To define the TTP ratio, let's denote:
	 TTP1 the time from treatment initiation to the time of progression after first irradiation
	TTP2 the time from first progression to the time of progression after the second SABR course. Due to the very poor prognosis of those patients, death without documented progression will be counted as progressions. Patients alive and free of progression at the cut-off date will be censored at the last assessment date. Radiological progression is measured using RECIST v1.1 on the same tumor lesions over all the

	trial, whenever p	possible.									

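### Second progression in PFS2, TTP2 and the TTP ratio is judged against the whole-study nadir, so a patient who first progressed on the target-lesion sum and then stays stable counts as progressed again at the 6-week CT

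*Protocol*

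**What the plan says.** Patients in the lung and sarcoma cohorts may receive a second SABR course once they have a first progression by RECIST 1.1 (Protocol 3.1, 5.2.2 and 6.3). Three secondary time endpoints follow.

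- **PFS2** is "measured from the date of the second SABR course to the date of second progression or death" (7.2.1).
- **TTP2** runs from first progression to progression after the second course.
- **TTPr** is TTP2 divided by TTP1, summarised at thresholds such as 1.33, 1.5 and 2 (8.3.2).

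Section 7.2.1 says how progression is assessed: "Radiological progression is measured using recist v1.1 on the same tumor lesions over all the trial whenever possible". The synopsis and section 2.2 carry the same rule.

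Appendix 4, Table 1.1, defines progression as "At least a 20% increase in the sum of diameters of target lesions, taking as reference the smallest sum on study", and adds that "the sum must also demonstrate an absolute increase of at least 5 mm". Stable disease uses the same reference: "taking as reference the smallest sum diameters while on study". New lesions count too: "The appearance of one or more new lesions is also considered progression".

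A CT is required 6 weeks after the second course (footnote 4 to Table 1). A later reference point appears for one second-course comparison only, the size change of irradiated versus non-irradiated lesions. It is taken from the second SABR in section 2.2 and from progression 1 in section 7.2.1.

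**The concern.** A patient enters the second-course analysis because RECIST 1.1 progression has already been met. If that happened through the target-lesion sum, the sum is already at least 20% and 5 mm above the nadir. With the same lesions and the same nadir, a patient in whom nothing further happens still satisfies the definition at the next scan.

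PFS2 then records when the scan took place, not how long disease was controlled after re-irradiation. TTP2 becomes the scan interval plus the wait for the second course, and TTPr becomes a rescaled reciprocal of TTP1. A second course that stabilised disease could look ineffective on all three endpoints.

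**Working it through.** The protocol states no sample size, power or success threshold for PFS2, TTP2 or TTPr, so there is no planned figure to reproduce. The check applies the written rule to assumed sums.

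**Inputs from the protocol.** Progression is an increase of at least 20% and at least 5 mm over the smallest sum on study (Appendix 4). The first CT is 6 weeks after the second course (Table 1). TTPr = TTP2/TTP1 (8.3.2).

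**Inputs assumed.** These are the lesion sums, the distribution of growth and shrinkage, and the gap g from first progression to the second SABR (0 to 6 weeks).

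**Step 1: single patients, unchanged sum at 6 weeks.**

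| Nadir (mm) | First progression (mm) | 6-week CT (mm) | Against nadir | Against first-progression sum |
|---|---|---|---|---|
| 50 | 60 | 60 | +20%, +10 mm: PD | 0%: not PD |
| 50 | 65 | 65 | +30%, +15 mm: PD | 0%: not PD |
| 80 | 100 | 100 | +25%, +20 mm: PD | 0%: not PD |
| 50 | 75 | 75 | +50%, +25 mm: PD | 0%: not PD |

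In the second row, a reference of 65 mm would put the progression threshold at 65 × 1.2 = 78 mm.

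**Step 2: shrinkage needed to leave progression.** If the sum at first progression is R times the nadir, it must shrink by more than 1 − 1.2/R. This is 0% for R = 1.2, 7.7% for 1.3, 14.3% for 1.4 and 20% for 1.5. A patient going 50, 75, 60 mm has shrunk by 20% and is still exactly +20% over the nadir, hence PD.

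**Step 3: share of target-sum progressors affected.** Assume R uniform on 1.2 to 1.5 and a proportional 6-week change d, normal with mean μ and SD 0.12. Sums are taken as large enough that the 5 mm condition does not bind. Simulated probabilities of PD at the 6-week CT:

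| Mean change μ | Against study nadir: R(1+d) ≥ 1.2 | Against sum at second SABR: d ≥ 0.20 |
|---|---|---|
| 0 | 79% | 5% |
| −10% | 52% | 0.6% |
| −20% | 24% | below 0.1% |
| −30% | 7% | below 0.1% |

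Moving the upper limit of R between 1.3 and 1.8 changes the nadir column to 63–89% at μ = 0 and 31–72% at μ = −10%.

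**Step 4: effect on the time endpoints.** If PD is called at the 6-week CT, PFS2 is about 6 weeks, TTP2 = 6 + g weeks, and TTPr = (6 + g)/TTP1.

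| TTP1 (weeks) | g = 0 | g = 3 | g = 6 |
|---|---|---|---|
| 6 | 1.0 | 1.5 | 2.0 |
| 12 | 0.5 | 0.75 | 1.0 |
| 24 | 0.25 | 0.38 | 0.5 |

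The scheduled CTs after the first SABR fall at weeks 7 and 13, about 6 and 12 weeks from treatment start. An affected patient with TTP1 of 12 weeks or more therefore cannot reach even the 1.33 threshold for any g up to 6 weeks.

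**Step 5: other routes to first progression.** If a new lesion defined first progression, the original-lesion sum may be below 1.2 times the nadir. Following only the original lesions, an unchanged patient is then not PD. Counting the lesion as still new relative to baseline makes the patient PD. The text supports either reading. For non-target progression, Appendix 4 gives no numeric reference, so the result is unclear.

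**The case against.** The strongest reply is that the sentence in 7.2.1 fixes which lesions are followed, and only whenever possible, while the nadir comes from a generic RECIST appendix that does not address assessment after progression. Other text suggests a sensible intent. A second progression is meant as a separate event, the lesion-size comparison is already re-referenced, and section 6.3 stops all treatment after second progression, which would make little sense if stable patients met it at their first scan. On this view the reference is simply open and belongs in the SAP.

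That makes the literal result unlikely to be what the authors wanted, but it does not supply another reference. The protocol names RECIST 1.1, its own appendix says what RECIST 1.1 compares with, and the flexibility concerns the lesions, not the nadir. A stated rule gives a wrong result here, so this is more than a detail left to the SAP.

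Other parts of the objection stand. A reader might infer that every stable patient, or every re-irradiated patient, is called progressed at 6 weeks. The documents do not support that: the result is firm only for target-sum progressors whose shrinkage is insufficient, and ablative treatment of progressing lesions may well shrink them. Nor does the problem touch the only decision rule for the second course, the 6-week response rate in section 8.1. PFS2, TTP2 and TTPr are secondary, and the TTPr cut-offs are descriptive.

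**Conclusion.** The point holds in a limited form. As written, a patient whose first progression came through the target-lesion sum, and whose sum then stays unchanged or does not fall below 1.2 times the nadir, meets progression again at the 6-week CT. For these patients the three endpoints carry scan timing and TTP1, not the effect of the second course. The direction follows from the protocol's text alone. The size does not: 79%, 52% and 24% rest on the assumed range for R, the 12% SD and the assumed mean shrinkage, and they leave out new-lesion and non-target progressors. Because the endpoints are secondary and descriptive, the definition should be corrected before analysis, but the primary result is unaffected.

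**What to change.** In sections 7.2.1 and 8.3.2, and for the analysis definition only:

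- Measure second progression as an increase of at least 20% and at least 5 mm over the smallest sum recorded from the last CT before the second SABR onward.
- Include the lesions that defined first progression in the followed set.
- Count as new only lesions absent from that CT.
- Apply the rule identically to PFS2, TTP2 and TTPr, and align the synopsis and section 2.2.

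The cost is one definition, applied to CTs already scheduled. A small downside is that the reference CT may precede the second SABR by some weeks.

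Section 6.3 ties discontinuation of all treatment to second progression, and the end-of-study visit it then prescribes lists no imaging. Where the literal rule was applied, later CTs may be missing. The sponsor must reconcile section 6.3 with the analysis definition; no clinical rule is proposed here.
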